5.4 Justification of Sample Size

We project that it will be feasible to recruit a total of 40 patients with histologically and/or clinically confirmed and/or suspected NET into the study. Each subject is expected to have on average 2 lesions and among the 80 total lesions; we project that 60% will be positive for NET. To evaluate the adequacy of the sample size (i.e., number of lesions), we computed the precision, as measured by the width of the 95% CI, with which the sensitivity and specificity of 68Ga-DOTATOC PET-CT scan can be estimated. The width of the 95% CI will be no greater than +/-14% for sensitivity and +/- 17% for specificity in the lesion-based analysis. For the patient-based analysis, the precision with which sensitivity can be estimated is +/- 15%.

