5.2. Interpretation of Data

The number of lesions that could be identified clearly as single focus will be determined for each patient. To enable a methodic and consistent approach to lesion identification, we will create 3 categories of lesion sites: organs (Head and Neck, lungs, breast, liver, pancreas, gastrointestinal tract, kidney, spleen, and pelvis/ovaries), nodal regions (Axillary, thoracic, mesenteric, abdominal, and pelvic [excluding mesenteric], and inguinal regions), and musculoskeletal system (vertebrae, bony thorax, bony pelvis, and limb bones). Because of confluence and inability to clearly delineate single liver lesions in some cases, liver metastases will be classified as 1 organ metastasis, independent of the number of liver metastases present. Lymph nodes smaller than 1 cm on CT or MRI and showing marked avidity for ⁶⁸Ga-DOTATOC will be labeled as positive for

disease. In cases where images from ¹¹¹In-Octreotide are available for comparison, the same imaging parameters will be applied. The presence of lesions will be confirmed by cross-sectional imaging of all patients with CT or MRI. As there may be lesion/s that can show abnormal focal activity on Ga-68 PET images but not on morphologic images, such lesion/s will be considered positive NET.

Each scan (⁶⁸Ga-DOTATOC) will be read by two independent, board certified nuclear medicine physicians blinded to the results of other scan. A third independent nuclear medicine physician will then review both the results (independent reviews) and clinical information to reach to a consensus.

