5.4 Statistical Analysis

The primary goal of the analysis is to estimate the diagnostic accuracy of 68Ga-DOTATOC PET-CT for detecting NET compared to conventional imaging techniques. Analyses will be performed with both patient and lesion as the unit of observation. Since all patients are expected to have at least one NET lesion, only sensitivity can be estimated in the analysis by patient, whereas both sensitivity and specificity will be estimated in the lesion based analysis. We will compute the relevant proportions and corresponding 95% confidence intervals, with adjustment for correlated data from the same patient. Results from pathology reports available from previous biopsy or surgical specimens will be considered the gold standard. In the absence of pathology reports, initial and follow up diagnostic CT or MRI scan following nonsurgical therapy including chemotherapy will be considered the gold standard.

Kappa statistics will be computed and McNemar's test will be performed to compare the sensitivity and specificity between ⁶⁸Ga-DOTATOC PET-CT with SPECT and diagnostic CT for detecting NET. All analyses will be performed in SAS and p-values < 0.05 will be considered statistically significant.

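### The lesion-level precision limits of ±14% and ±17% assume independent lesions, but the reported intervals will be adjusted for within-patient correlation

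*Combined protocol and SAP*

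**What the plan says.** Section 5.4, Justification of Sample Size, takes the number of patients from feasibility: "We project that it will be feasible to recruit a total of 40 patients". It then projects the lesion counts: "Each subject is expected to have on average 2 lesions and among the 80 total lesions; we project that 60% will be positive for NET". That gives 48 NET-positive and 32 NET-negative lesions. Adequacy is judged by precision, and the result is given as an upper limit: "The width of the 95% CI will be no greater than +/-14% for sensitivity and +/- 17% for specificity in the lesion-based analysis". The section mentions no intracluster correlation, design effect or effective number of lesions.

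Section 5.4, Statistical Analysis, says the proportions will be reported with "corresponding 95% confidence intervals, with adjustment for correlated data from the same patient". It names no method for the intervals or for the adjustment. It also states: "Since all patients are expected to have at least one NET lesion".

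Section 5.2 sets the counting rule: "The number of lesions that could be identified clearly as single focus will be determined for each patient". Liver metastases are the exception and count as one. A patient can therefore contribute several lesions.

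**The concern.** The precision statement and the planned analysis rest on different variance assumptions. One treats the lesions as independent. The other will allow for several lesions coming from the same patient.

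This matters because the aim is estimation and N was set by feasibility, so the precision paragraph is the only statistical argument that 40 patients are enough. A reader will take ±14% and ±17% as ceilings on the intervals in the final report. If they are ceilings only for an analysis that will not be done, the claim is wrong as written, even if the precision achieved proves acceptable.

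**Working it through.** **Inputs.** From section 5.4: 40 patients, 80 lesions, 60% positive (48 positive, 32 negative), 95% confidence, at least one NET lesion per patient. Assumed, because the documents give neither: ICC of 0.2 to 0.5, and the spread of lesions over patients.

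**Step 1: reproduce the plan's figures.** Wald half-width = 1.96 × √(p(1 − p)/n) at p = 0.5.

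- Sensitivity, n = 48: 1.96 × √(0.25/48) = 14.14% (stated 14%)
- Specificity, n = 32: 1.96 × √(0.25/32) = 17.32% (stated 17%)
- Patient level, n = 40: 1.96 × √(0.25/40) = 15.49% (stated 15%)

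All three match after rounding. Wilson intervals give 13.61%, 16.37% and 14.80%. The lesion figures are thus the maxima for independent lesions. Even allowing for rounding (up to 14.5% and 17.5%), the Wald figures leave room for a design effect of only 1.05 and 1.02.

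**Step 2: must lesions cluster?** For positive lesions, yes: 48 lesions in 40 patients, each with at least one, means some patients have two or more. The mildest pattern is 32 patients with one and 8 with two. For negative lesions clustering is possible but not forced, since 32 patients could have one each.

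**Step 3: add the design effect.** DEFF = 1 + (Σm²/Σm − 1) × ICC, where m is the number of lesions a patient contributes to the denominator. Wald half-width = 1.96 × √(p(1 − p) × DEFF/n); for Wilson, replace n by n/DEFF. Every pattern below is compatible with 80 lesions in 40 patients and at least one positive lesion each. For example, 16 patients with one positive and two negative, 16 with one positive, and 8 with two positive give 48 positive and 32 negative.

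Half-widths at p = 0.5, for ICC 0.2 to 0.5:

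| Pattern | Σm²/Σm | DEFF | Wald | Wilson |
|---|---|---|---|---|
| Sensitivity: 32 patients with 1, 8 with 2 | 64/48 = 1.333 | 1.067 to 1.167 | 14.6 to 15.3% | 14.0 to 14.6% |
| Sensitivity: 36 with 1, 4 with 3 | 72/48 = 1.5 | 1.10 to 1.25 | 14.8 to 15.8% | 14.2 to 15.1% |
| Specificity: 32 with 1 | 32/32 = 1 | 1 | 17.3% | 16.4% |
| Specificity: 16 with 1, 8 with 2 | 48/32 = 1.5 | 1.10 to 1.25 | 18.2 to 19.4% | 17.1 to 18.1% |
| Specificity: 16 with 2 | 64/32 = 2 | 1.2 to 1.5 | 19.0 to 21.2% | 17.7 to 19.5% |

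Beta-binomial simulation (20,000 runs, cluster-robust standard errors, p = 0.5, ICC 0.2 / 0.5) agrees: mean half-widths of 14.6 / 15.2% for the first row, 18.0 / 19.2% for the fourth and 18.9 / 21.1% for the fifth.

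**Step 4: when are the limits passed?** Wilson at p = 0.5 exceeds 14% once DEFF passes 1.063 (ICC 0.19 in the mildest pattern). It exceeds 17% once DEFF passes 1.089 (ICC 0.18 with 8 patients having two negative lesions, 0.09 with 16). By Wald, the mildest sensitivity pattern exceeds 14% only for a true sensitivity of about 36 to 64% (ICC 0.2) or 30 to 70% (ICC 0.5).

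**Step 5: likely accuracy.** At 90%, the largest Wald DEFF within the limits is 2.72 for sensitivity and 2.67 for specificity. The mildest sensitivity pattern then gives 8.8 to 9.2%.

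**The case against.** The strongest reply is that the limits would probably hold in practice. The background section quotes high accuracy for these tracers: section 2.3 gives a patient-level sensitivity of 97% and specificity of 92% for one 68Ga-DOTATOC study. The least favourable lesion-level figure is a 74.3% detection rate in a 68Ga-DOTATATE study of patients with negative or equivocal octreotide scans. At 74.3%, the heavier sensitivity pattern above with ICC 0.5 gives 13.8%, still inside ±14%. At a specificity of 92%, 16 patients with two negative lesions and ICC 0.5 give 11.5%, well inside ±17%.

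Other parts of the reply also stand. With no clustering, Wald is already slightly above the stated limits, so part of the excess is rounding; the clustering itself adds about 0.5 to 1.1 points to sensitivity in the mildest pattern. With Wilson and ICC 0.2, that pattern gives 14.0% and the middle specificity pattern 17.1%, which round to the stated limits. The specificity inflation depends on an assumed spread of negative lesions. The plan sets no target precision that a move from 14% to 15% would miss.

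These points limit the consequence but do not rescue the statement. The paragraph gives no anticipated accuracy; it gives a maximum, and its figures are those of the worst case. The maximum has to hold there for the intervals that will be reported, and under positive correlation it does not.

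**Conclusion.** The concern holds. The lesion-level limits are maxima for independent lesions, while the plan promises intervals adjusted for correlation. At p = 0.5 and an assumed ICC of 0.2 to 0.5, the excess over the stated sensitivity limit is about 0.6 to 1.3 points by Wald in the mildest pattern (14.6 to 15.3% against 14%) and 0 to 0.6 by Wilson. For specificity, clustering adds nothing if no patient has two negative lesions. If 16 patients have two each, the excess reaches about 4 points by Wald (21.2% against 17%).

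The sensitivity result needs only a positive ICC and the plan's own lesion counts. The specificity result also needs some patients to have two or more negative lesions, which an average of two lesions per patient allows. The fault lies in the claimed ceiling rather than in the precision likely to be obtained. The patient-level ±15% is unaffected, since each patient counts once.

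**What to change.** In section 5.4, Justification of Sample Size:

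1. Name the interval method, including how it handles lesions from the same patient.
2. State the expected spread of positive and negative lesions over patients, and give the half-widths at ICC 0, 0.2 and 0.5, both at p = 0.5 and at the anticipated accuracy.
3. Remove the upper-limit wording, or restrict it to independent lesions.

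An illustration by Wald, with 8 patients having two positive lesions and 8 having two negative (the rest of each count one per patient):

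| | ICC 0 | ICC 0.2 | ICC 0.5 |
|---|---|---|---|
| Sensitivity, p = 0.5 | 14.1% | 14.6% | 15.3% |
| Specificity, p = 0.5 | 17.3% | 18.2% | 19.4% |
| Sensitivity, p = 0.9 | 8.5% | 8.8% | 9.2% |
| Specificity, p = 0.9 | 10.4% | 10.9% | 11.6% |

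The least that would cure the overstatement is a clause saying that the figures assume independent lesions at p = 0.5. The short table is better because it describes the intervals that will be reported. The cost is one reworded paragraph with slightly less favourable figures. No patients are added and the analysis stays the same.

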6.0 Criteria for Study Termination

The IND/study will be stopped if any adverse reaction >grade 1 is observed during the trial. A full assessment of adverse reaction will be conducted to determine if it is drug related or not drug related. If the adverse reaction is not related to the drug, the study will be resumed and further

patients will be recruited. If the adverse reaction is found to be drug related, it will be reported to the IRB and FDA according to respective schedule.

The toxicity/adverse event will be evaluated according to Common Terminology Criteria for Adverse Events (CTCAE) Version 4.0, published by NIH. The scale of toxicity is 1 to 5, with 1 being mild adverse event and 5 being death. The details of the scale can be found at http://evs.nci.nih.gov/ftp1/CTCAE/CTCAE 4.03 2010-06-14 QuickReference 5x7.pdf , which is specified in the CRF.

7.0 Monitoring and Quality Control / Assurance

This study will be monitored at all stages by the clinical research personnel designated by the physician. Monitoring will include personal visits and telephone communication to ensure that the investigation is conducted according to the Protocol and complies with GCP guidelines and applicable regulatory requirements. On-site review of CRFs will include a review of forms for completeness and clarity, and consistency with source documents available for each patient.

Any data recorded directly in the CRF, for which no other written or electronic record will be maintained in the patient's medical record, will be considered source data and should be signed by the Investigator (e.g. results of physical examinations, vital signs testing, or the investigational product administration procedure). During monitoring visits the data recorded in the CRFs, source documents, and other study-related records will be compared against each other in order to ensure accurate data that reflect the actual experience of the patient in the study, i.e. source data verification. The Investigator must ensure that the clinical notes will be available for direct verification of source data.

To this end, the Investigator agrees to allow regular visits (frequency depending on recruitment, but estimated as four-weekly) by the study monitors and to ensure they have a suitable area in which to work (e.g. a desk) and adequate access to study personnel and documents.

Medical monitors and clinical research associates (CRAs) or assistants may request to witness patient evaluations occurring as part of this Protocol. The Investigator and appropriate personnel will be periodically requested to attend meetings/workshops to ensure acceptable Protocol execution, if deemed necessary.

The study may be audited or inspected by the Regulatory or Health Authority or IEC/IRB. If such an audit or inspection occurs, the Investigator must agree to allow access to the study site, required patient records and study documents. By signing this Protocol, the Investigator grants permission to personnel mentioned in this protocol and appropriate Regulatory Authorities for onsite monitoring of all appropriate study documentation, as well as on-site review of the procedures employed in the CRF generation, where clinically appropriate. The Investigator will be informed about the outcome of the audit.

The following activities will be undertaken to ensure the quality of trial-related activities:

- adherence to the trial site standard operating procedures to maintain accurate and consistent practices and procedures
- conduct of a site initiation visit to ensure the Investigator and all personnel involved in the trial understand the Protocol, including the study procedures and their responsibilities
- completion of a standard CRF in accordance with GCP requirements to ensure accurate and reliable data

• Periodic monitoring to ensure the trial data are accurate, complete and verifiable from source documents, and that the Protocol is being followed.

8.0 Patient Consent and Peer Review

Informed consent will be obtained for each patient prior to being placed on this study. Approval by the institutional review board is necessary before beginning this protocol. Please find appendix (b) for a copy of patient consent.

9.0 Data Safety and Monitoring Boards

This trial will be monitored by the Albert Einstein Cancer Center Data Safety Monitoring Committee (AECC DSMC). A copy of the monitoring plan is maintained at the CPDMU. The DSMC as part of its function performs quarterly reviews of Clinical Trials Compliance Audits, monthly reviews Adverse Events Reports, and monthly reviews of internally monitored Phase I/Phase II trials for accrual and response. Other monitoring activities are established as necessary in a protocol specific manner.

The details of the monitoring are outlined in the AECC Data and Safety Monitoring Plan policy document.

9.1 Trial Monitoring

This trial will be monitored by the Albert Einstein Cancer Center Data Safety Monitoring Committee (AECC DSMC). A copy of the monitoring plan is maintained at the CPDMU. The DSMC as part of its function performs quarterly reviews of Clinical Trials Compliance Audits, monthly reviews Adverse Events Reports, and monthly reviews of internally monitored Phase I/Phase II trials for accrual and response. Other monitoring activities are established as necessary in a protocol specific manner.

This trial will be part of the monthly Quality Assurance Audits. Each patient will be evaluated within 8 weeks of registration. This permits evaluation of consent, eligibility, and treatment/dose modification/Adverse Event (AE) reporting, and data quality for the first cycle (or month) of treatment.

This trial may also be eligible for quarterly Quality Enhancement Audit. Each audit consists of a review of regulatory documents, pharmacy drug accountability (if applicable) and patient case review, confirming eligibility, protocol compliance and source documentation

The results of the audit will be presented at the following month's DSMC meeting. The DSMC has the authority to close trial to patient accrual should the risk to patients be excessive or results require a corrective plan from the Principal Investigator. All study suspensions and closures will be forwarded to the IRB and study sponsor. All audit reports are forwarded to the DSMC and presented to the DSMC by the Audit Committee Coordinator.

